### 3.2 Device Usage and Safety

The SinuSonic consists of a fully-disposable medical grade silicone nosepiece mounted to a resin body. The device is equipped with a flutter valve located at the top of the device which creates gentle, self-guided oscillating expiratory resistance.

The SinuSonic is a legally marketed device used in accordance with its labeling. It is substantially equivalent to many Class I OTC devices with the same intended use and indications for use in clearing mucus to improve air flow, such as the Navage Nose Cleaner.

## 4.0 Inclusion and Exclusion Criteria/Study Population

### Inclusion Criteria

- Adults 18 years or older with no transient symptoms of any URI or allergies at baseline.

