## 3.0 Intervention to be studied

Subjects will be screened for likely inclusion during the summer months. Baseline demographics, medical comorbidities, and URI symptoms will be assessed. Informed consent will be completed.

The fall URI season typically runs through September and October (Turner R et al). Towards the end of screening, all subjects will be randomized 2:1 to active use of Sinusonic (128Hz) for 1 minute 3 times daily or an identical “placebo” device that emits a frequency of 1,000 Hz and has the ball valve modified to eliminate positive expiratory pressure. Devices will be shipped to home addresses via overnight mail. On September 1, 2020 all subjects will begin daily use of their assigned device. Subjects will remain blinded as to treatment arm until study completion.

Subjects will be asked to complete a brief daily questionnaire on URI symptoms and whether or not they feel as if they have a “cold”. Previously validated questions for viral URI studies are rating 8 items on a likert scale from 0 (no symptoms) to 3 (severe symptoms) (Jackson GG, et al). The 8 symptoms are: sneezing, runny nose, nasal obstruction, sore throat, cough, headache, malaise, and chilliness. A Total Symptom Score (TSS) will be the sum of each symptom to provide a daily score ranging from 0 to 24. Prior studies have defined the common cold as present when:

- 1)  $TSS \geq 14$  PLUS moderate or severe nasal discharge x 3 days OR patient subjective impression they have a cold OR

2) TSS < 14 AND moderate or severe nasal discharge x 3 days AND subjective impression they have a cold

Answers will be uploaded to secure REDCAP database. The study duration is 8 weeks. At the end of the study, subjects will be asked questions regarding device safety and tolerability.

Our primary outcome will be absolute number of URIs experienced during the 8 week study period. Secondary outcomes will be time to first URI, duration and symptom severity of viral URIs. These metrics will allow us to determine if Sinusonic decreases the frequency of URIs, as well as potentially shortening the duration or decreasing the severity of URIs.

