### Exclusion Criteria

Any transient ENT condition that may impact upper airway to include acute sinusitis or otitis.

Any upper respiratory illness within last 2 weeks

TSS will be measured at baseline as described above and must be <9 for inclusion (Eccles etal).

Topical decongestant use in last week

Current nasal crusting or history of ulceration or perforation

History of severe nose bleeding within last 3 months

Known pregnancy

Immunosuppressed condition or on immune modulating medications such as prednisone or chemotherapy

Allergic sensitivity to silicone or any other component of device

Inability to read and understand English

Inability to perform treatment due to underlying medical condition

After confirming that subjects meet inclusion criteria, they will be entered into study as outlined below. Subjects who have URI symptoms at the beginning of the study will specifically be excluded, as the purpose of the study is prevention of URIs, not treatment of pre-existing URIs.

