#### **4.1 COVID19**

The purpose of the study is to see if Sinusonic prevents community acquired viral URIs, not to treat existing infections. So patients must be asymptomatic at the beginning of study. As this study is not conducted exclusively on MUSC patients and is being done virtually (to minimize exposure and increase safety during the covid pandemic), we do not have the ability to perform widespread covid testing on hundreds of asymptomatic patients. So it is possible that someone will have undiagnosed covid.

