#### **7.0 Recruitment Methods**

We will publicize the study through MUSC and Sinusonic social media targeting geographic regions described above. A number and email will be provided for subjects interested in participating. Only one subject per household can be enrolled.

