## APPENDIX

### **SCREENING CRITERIA (all must be no):**

QUESTIONS	YES	NO
Have you had sinusitis, otitis or laryngitis or any other upper respiratory illness in the last 2 weeks?		
Have you used topical nasal decongestant spray in the last week?		
Do you currently have nasal crusting or history of ulcers or perforation?		
Have you had severe nasal bleeding in the last 3 months?		
Are you pregnant?		
Are you allergic or sensitive to silicone?		
Do you have any underlying medical condition that would prevent your ability to perform treatment?		
Are you immunosuppressed or on immunosuppressant medications, such as prednisone or chemotherapy agents?		

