### COMORBID MEDICAL CONDITIONS: Check box and provide details if present

 Obstructive Sleep Apnea:	 Currently being treated	 History / No current treatment
 Allergic rhinitis:		
 Previous allergy testing (blood test or skin prick):	 Yes	 No
 Immunotherapy shots for allergies:	 Yes	 No
 Non-allergic rhinitis	 Yes	 No
 Asthma	 Yes	 No
 Chronic rhinosinusitis	 Yes	 No
 Nasal polyps	 Yes	 No
 Prior ear/sinus surgery	 Yes	 No
 Migraine headache history:	 Resolved/past diagnosis	 Present/medicated
<hr/>		
 Height (ft/in):		
 Weight (lbs):		

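### Persistent nasal symptoms are not clearly excluded and the URI rule ignores each subject's baseline, so relief of rhinitis could be counted as URI prevention

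*Combined protocol and SAP*

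**What the plan says.** **Eligibility.** The inclusion criterion is "Adults 18 years or older with no transient symptoms of any URI or allergies at baseline". The Exclusion Criteria bar "Any transient ENT condition that may impact upper airway to include acute sinusitis or otitis" and add "TSS will be measured at baseline as described above and must be <9 for inclusion". The paragraph closing that section also rules out people with URI symptoms at the start, and Section 4.1 states "So patients must be asymptomatic at the beginning of study". Sections 9.1 and 18.0 show that the TSS limit is what is rechecked before randomisation; Section 18.0 adds that there must be no active URI.

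**Screening and baseline forms (Appendix).** The checklist asks "Have you had sinusitis, otitis or laryngitis or any other upper respiratory illness in the last 2 weeks" but has no item on allergy symptoms or chronic nasal disease. The comorbidity form lists "Chronic rhinosinusitis", allergic rhinitis, non-allergic rhinitis and nasal polyps. These are recorded; none is an exclusion.

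**Case rule (Section 3.0).** Route 1 is TSS of 14 or more "PLUS moderate or severe nasal discharge x 3 days OR patient subjective impression they have a cold OR" the second route. Route 2 is TSS below 14 with moderate or severe discharge for 3 days and the subject's own impression of a cold. Neither refers to baseline, and no virological confirmation is specified.

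**Device effect.** Section 1.0 cites a chronic rhinitis trial in which congestion and drainage improved. Section 2.0 says roughly 80% of its patients improved.

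**Analysis.** Section 10.0 plans no adjustment, stratification or sensitivity analysis for baseline TSS or rhinitis.

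**The concern.** The endpoint is meant to count new viral infections, but one of its components, nasal discharge, is a symptom that the device is said to relieve in people who have no infection. If people with persistent discharge enter, some will already satisfy the discharge part of the rule on an ordinary day. One yes to the cold question then makes a URI.

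Randomisation balances the number of such people between arms. It does not balance the false cases they produce, because relief of rhinitis would happen after randomisation and could differ by arm. A trial with no effect on infection could then show fewer URIs on the active device, and the result would be read as support for the prevention hypothesis.

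**Working it through.** **1. The plan's own figure.** Section 5.0 gives 200 active and 100 sham subjects to detect a fall from 50% to 33%. Taking two-sided alpha 0.05 and 80% power (neither sidedness nor power is stated), the two-proportion formula at 2:1 gives 98 + 196 = 294. At 100 and 200, power is 81.2%. The plan's figure reproduces, and the same test is used below.

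**2. What the baseline limit lets through.** Take the three nasal items (sneezing, runny nose, obstruction), each 0 to 3, with the other five at 0. There are 4 × 4 × 4 = 64 patterns. TSS below 9 removes only 3 + 3 + 3 = 9, so 63 pass. Runny nose of 2 or 3 occurs in 2 × 16 = 32 patterns, less the one removed, so 31 of the 63 already carry moderate or severe discharge. For example, runny nose 2, obstruction 3 and sneezing 2 give TSS 7. The TSS limit does not stop this subject; the statements on URI symptoms and on being asymptomatic might.

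**3. Which route such a subject can take.** I read route 1 as TSS of 14 or more together with either discharge or a self-judged cold. The nasal items sum to at most 9, so rhinitis alone cannot reach 14. A rhinitis-only case must come through route 2: habitual discharge of 2 or 3 for three days, plus a yes to the cold question. Route 2 has no minimum TSS.

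**4. Possible size, with no effect on true URIs.** All inputs except the 50% URI rate and the sample sizes are assumptions; the documents give no rhinitis share and no false-case risk. Let r be the share with rhinitis and m the risk of a false URI among rhinitis subjects who have no true URI.

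- Observed rate in an arm = (1 − r) × 0.5 + r × [1 − 0.5 × (1 − m)] = 0.5 + 0.5 × r × m.
- Gap = 0.5 × r × (m sham − m active).
- The chance of significance in favour of active is Φ[(gap − 1.96 × s0)/s1], where s0 is the pooled and s1 the unpooled standard error at 100 and 200. The opposite tail is added for the two-sided rate.

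Worked line, r = 0.30, m = 0.75 and 0.25: rates 0.6125 and 0.5375; pooled rate (61.25 + 107.5)/300 = 0.5625; s0 = √(0.5625 × 0.4375 × 0.015) = 0.0608; s1 = √(0.6125 × 0.3875/100 + 0.5375 × 0.4625/200) = 0.0601. Then (0.075 − 0.1191)/0.0601 = −0.73, a probability of 23%.

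| r | m sham / active | Sham | Active | Gap (points) | Two-sided rate |
|---|---|---|---|---|---|
| 15% | 30% / 20% | 52.25% | 51.5% | 0.75 | 5.2% |
| 15% | 60% / 40% | 54.5% | 53.0% | 1.5 | 5.7% |
| 30% | 75% / 25% | 61.25% | 53.75% | 7.5 | 23% |
| 45% | 75% / 25% | 66.9% | 55.6% | 11.25 | 46% |

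Exact binomial calculation gives 24% and 47% for the last two rows and leaves the first two at 5% to 6%. In the second row, 4.3 of the 5.7 points favour the device.

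**5. A second parameterisation.** Suppose a true URI rate of 33% in both arms, 20% with rhinitis, a false-case risk of 50% in sham, and 80% of those cases removed by the device. Sham is 0.33 + 0.67 × 0.2 × 0.5 = 39.7%; active is 0.33 + 0.67 × 0.2 × 0.5 × 0.2 = 34.3%. The chance of significance favouring active is 14.9%, against a nominal 2.5%. With true rates of 33% or 50%, shares of 10% to 50%, sham risks of 20% to 50% and removal of 50% to 80%, that chance runs from 3% to 60%.

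**The case against.** **Eligibility is not settled.** Section 4.0 excludes people with URI symptoms at the start and Section 4.1 says asymptomatic. The diary items are described as URI symptoms, so a strict reader could turn the TSS 7 example away, with the TSS limit only an extra condition. This stands: one might infer that such a subject is definitely eligible, but the documents only leave it open. Transient allergy symptoms are barred outright, so the issue is confined to persistent ones.

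**The subject must also report a cold.** Someone with daily rhinitis may seldom call the usual state a cold. This stands, and the documents give no frequency.

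**A differential effect is not established.** A reader might infer that false cases would fall in the active arm only. Sections 1.0 and 2.0 report improvement in a rhinitis trial but do not say it was controlled or that benefit exceeded a sham. A sham used three times daily under blinding could also change self-reported symptoms. The supportable wording is that false cases could fall more in the active arm.

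**Recruitment.** Section 7.0 says "We will publicize the study through MUSC and Sinusonic social media", which may suggest an intake rich in chronic nasal disease. The text says nothing about who responds, so the point does not rest on this.

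**Size and stage.** The large figures need a high rhinitis share together with a 75% false-case risk in sham. The calculation also uses the proportion with a URI, while the primary outcome is the number of URIs. The study is a pilot with an exploratory analysis and borrows its case definition from prior studies. All of this limits the weight of the point, but none of it supplies a baseline reference or a planned check.

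**Conclusion.** The point holds in limited form. Persistent nasal symptoms are not clearly excluded, both case routes use absolute scores, and the protocol itself says the device improves a symptom that enters the case rule. Followed as written, the plan could count rhinitis relief as URI prevention, and nothing in Section 10.0 would reveal it.

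The two-sided false-positive rate could be anywhere from close to nominal (about 5%) to 24% or 47%, depending wholly on assumed rhinitis shares and false-case risks. The documents do not support saying that the bias is present or that it is large. They support saying that its direction, if present, would probably favour the device, and that a cheap check is missing. The conflict between the TSS limit and the asymptomatic requirement needs reconciling whatever the size of the bias.

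**What to change.** In Section 10.0, before unblinding:

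1. Pre-specify the primary comparison with and without subjects who have recorded allergic rhinitis, non-allergic rhinitis, chronic rhinosinusitis or nasal polyps, or a baseline runny-nose rating of 2 or more.
2. Pre-specify a sensitivity count in which the discharge limb needs a moderate or severe rating that is also at least one category above the subject's own baseline. Leave out subjects with baseline discharge 3, who cannot rise. The rule for subjects with baseline 0 or 1 is unchanged, so a habitual 1 drifting to 2 would still count.
3. Adjust the primary comparison for baseline TSS and recorded rhinitis. This improves precision; it does not remove a bias that arises from symptom relief after randomisation, so items 1 and 2 carry the weight.

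Reconcile the Inclusion Criteria, the Exclusion Criteria and Section 4.1 on which baseline symptoms are allowed.

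**Cost.** Analysis-plan wording and re-runs of the count. The Day 1 questionnaire and the comorbidity form already collect the data, and schedule and sample size are unaffected. The sensitivity analyses will have slightly fewer subjects and episodes, and a single baseline rating will not capture day-to-day variation in rhinitis.

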### Exclusion Criteria

Any transient ENT condition that may impact upper airway to include acute sinusitis or otitis.

Any upper respiratory illness within last 2 weeks

TSS will be measured at baseline as described above and must be <9 for inclusion (Eccles etal).

Topical decongestant use in last week

Current nasal crusting or history of ulceration or perforation

History of severe nose bleeding within last 3 months

Known pregnancy

Immunosuppressed condition or on immune modulating medications such as prednisone or chemotherapy

Allergic sensitivity to silicone or any other component of device

Inability to read and understand English

Inability to perform treatment due to underlying medical condition

After confirming that subjects meet inclusion criteria, they will be entered into study as outlined below. Subjects who have URI symptoms at the beginning of the study will specifically be excluded, as the purpose of the study is prevention of URIs, not treatment of pre-existing URIs.

#### **4.1 COVID19**

The purpose of the study is to see if Sinusonic prevents community acquired viral URIs, not to treat existing infections. So patients must be asymptomatic at the beginning of study. As this study is not conducted exclusively on MUSC patients and is being done virtually (to minimize exposure and increase safety during the covid pandemic), we do not have the ability to perform widespread covid testing on hundreds of asymptomatic patients. So it is possible that someone will have undiagnosed covid.

#### **5.0 Number of Subjects**

Prior research reports (Turner etal) using identical outcome measures and studying community acquired URIs in the fall season report that approximately 60% of subjects suffered from a viral URI (range 48% to 75% in each arm). We are planning to include 300 subjects (200 active device, 100 sham device). If we conservatively assume that only 50% of sham device subjects get an URI, we will be powered to detect a decrease to 33%.

#### **6.0 Setting**

Research will be conducted at geographical locations in the Southeast (SC, NC, GA, VA) that have similar fall viral URI seasons. Potential participant screening for all subjects across all aims, as well as informed consent and baseline evaluations, will occur remotely to avoid any risk to research personnel. All baseline and follow-up measures will be collected remotely using REDCap at 4 and 8 weeks.

#### **7.0 Recruitment Methods**

We will publicize the study through MUSC and Sinusonic social media targeting geographic regions described above. A number and email will be provided for subjects interested in participating. Only one subject per household can be enrolled.

## **8.0 Consent Process**

Patients who respond to social media recruitment will be contacted by study personnel to determine eligibility. As the goal is to recruit subjects from throughout the southeast, no in person visits will be conducted at MUSC and it will be necessary to obtain remote informed consent.

The remote consent process will include an informed consent discussion with the potential participant and involve the participant signing and returning the informed consent document to the researcher. The informed consent discussion will occur over the phone. The documentation of consent process will include sending the informed consent document to the subject for signature and transmitting it back to the research team to be signed by the researcher before any research procedures begin. The document will be sent using the electronic consent option in REDCap.

A member of the study team will describe in full detail the study and the informed consent form to the potential subject. The study team member will explain:

1. What would be different if the patient participated in the study versus receiving standard of care treatment.
2. The study is voluntary participation, patient may withdraw any time, and PI may take patient off study at any time.
3. The reason for doing the study
4. How many people will be in the study
5. Who is eligible to participate in the study
6. Details regarding the study device.
7. What medical assessments/questionnaires they will have and how often
8. Risks involved in participating in a study
9. What information will be gathered

The prospective participant will be given adequate time to review the informed consent form and ask any questions that they have before the consent is obtained. Participants will electronically be sent a signed copy of the ICF.

## **9.0 Study Design / Methods**

This study is designed as a pilot study.

Data will be collected by the study investigators as well as the subjects themselves throughout the entirety of the study. The data will consist of answers from subjects for questionnaires asked by the clinicians as well as self-reported answers from the subjects.

### **9.1 Schedule of Events**

All subjects (N=300)	Screening	Baseline assessment	Study start	Study endpoint
Date	Up to -30 Days	Day 1	12 Days	60 Days
Informed consent	X			
Inclusion/exclusion criteria	X	Reconfirm TSS<9		
Medical history	X			
Randomization (2:1 active:sham)		X		
Distribution of Sinusonic		X		
Viral URI questionnaire		X	X	X
Safety questions				X

## 10.0 Data Management

All analyses and graphs will be performed with SPSS 24.0, Sample Power 3.0, and Sigma Plot 10.0 (SPSS, Chicago, IL.). Disease information and demographic variables, such as age, gender, race, and VAS scores will be summarized using frequencies, means, and standard deviation as appropriate. Our primary outcome metric is number of viral URIs as defined above. Secondary outcome metrics include average duration of URIs and severity of symptoms (as measured by TSS) of URIs. Categorical variables will be compared using Chi Square or McNemar's test. Continuous variables will be compared using One-Way ANOVA with repeated measures follow by post-hoc analysis. Data regarding safety and patient satisfaction will be summarized for each time point. A p-value  $\leq 0.05$  will be considered statistically significant. Due to the exploratory nature of this study, no p-value correction (ie Bonferroni) will be applied.

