**Baseline medical history and exam****SinuSonic Study**

PI: [name]

Subject ID#: \_\_\_\_\_ Subjects Initials: \_\_\_\_\_

**DEMOGRAPHIC AND CLINICAL VARIABLES (If not previously collected):****Age at enrollment (years):** \_\_\_\_\_

--	--

**Gender:**      Male      Female**What is/was your profession (current/retired)?** \_\_\_\_\_

Do you have significant daily contact with young children (age under 12 years)? Yes / No

Do you fly frequently, ie more than twice per month? Yes / No

**LANGUAGE, ETHNICITY, RACE, MARITAL STATUS****Please mark one of the following categories which describes your native language:**

American English  
 Other: please specify \_\_\_\_\_

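### Section 10.0 gives no analytic use to plausible URI predictors already collected at baseline; prespecified adjustment would be a small, low-cost gain in precision (minor)

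*Combined protocol and SAP*

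**What the plan says.** **Analysis.** Section 10.0 (Data Management) is the whole analysis plan. For categorical variables it says "Categorical variables will be compared using Chi Square or McNemar's test"; for continuous variables it names a one-way ANOVA with repeated measures and post-hoc comparisons. Demographic and disease variables are to be described by frequencies, means and standard deviations. No covariate-adjusted model appears in any section, and no listed test is assigned to the primary outcome, which Section 3.0 defines as a count of URIs over 8 weeks. The significance rule is "A p-value $\leq 0.05$ will be considered statistically significant", with no statement of one or two sides.

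**Randomisation.** Section 3.0 says "all subjects will be randomized 2:1 to active use of Sinusonic (128Hz"), and the schedule in Section 9.1 repeats the ratio. Neither names a stratification factor or the method of randomisation.

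**Covariates collected.** The Appendix baseline form asks "Do you have significant daily contact with young children (age under 12 years") and "Do you fly frequently, ie more than twice per month". It also records smoking, nasal and allergy medication, and conditions such as allergic rhinitis, asthma and chronic rhinosinusitis. Baseline TSS is measured for eligibility (Section 4.0, reconfirmed in Section 9.1). No section says how any of these enters the comparison of arms.

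**Sample size.** Section 5.0 plans 300 subjects, 200 on the active device and 100 on sham. It takes a sham-arm URI risk of 50% as a cautious assumption, and its claim for the active arm is that "we will be powered to detect a decrease to 33" percent. The power level is not given.

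**The concern.** The child-contact and flying questions have an obvious exposure rationale. Chronic nasal disease and baseline symptoms can plausibly affect an endpoint built from nasal and systemic symptom scores and a subjective impression of having a cold. If such variables do predict URIs, leaving them out of the model gives up some precision. It also leaves any imbalance that happens to arise in the realised sample unaddressed, and with only 100 sham subjects and no stated stratification a noticeable gap is possible.

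There is also a prespecification issue. If a visible imbalance appears, the team may want to adjust after seeing the data, and readers could not tell a planned covariate set from a chosen one. Fixing the list now removes that choice. It is worth doing in a plan that already declines any multiplicity correction.

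**Working it through.** **Inputs from the documents.** Sham risk 0.50, active risk 0.33, arms of 100 and 200 (Section 5.0); alpha 0.05 (Section 10.0). **Assumed:** two-sided test, 80% target power, and every covariate prevalence and strength, since the documents give none.

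**1. Reproducing the plan's figure.** A pooled-variance comparison of two proportions at 1:2 allocation, 80% power and two-sided 0.05 needs 98 + 196 = 294 subjects, against 300 planned. Power at 300:
- pooled risk = (50 + 66)/300 = 0.3867
- SE under the null = √(0.3867 × 0.6133 × (1/100 + 1/200)) = 0.0596
- SE under the alternative = √(0.25/100 + 0.2211/200) = 0.0600
- power = Φ((0.17 − 1.96 × 0.0596)/0.0600) = Φ(0.884) = 81.2%

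The stated design therefore reproduces without any adjustment.

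**2. Power with adjustment (approximation).** Multiply both variances by (1 − R²), where R² is the share of outcome variance that the covariates explain. The equivalent unadjusted sample size is 300/(1 − R²).

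| Assumed R² | Power | Equivalent N |
|---|---|---|
| 0 | 81.2% | 300 |
| 1% | 81.6% | 303 |
| 2% | 81.9% | 306 |
| 5% | 83.1% | 316 |
| 10% | 85.0% | 333 |

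For one binary covariate with prevalence 20–40%:
- odds ratio 1.5: R² 0.6–0.9%, power 81.4–81.5%
- odds ratio 2: R² 1.9–2.7%, power 81.9–82.2%
- odds ratio 3: R² 4.7–6.6%, power 82.9–83.7%
- odds ratio 4: R² 7.3–10.2%, power 83.9–85.1%

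**3. Simulation for any URI (yes/no).** 3,000 trials per setting, 100:200, marginal risks 50% and 33%, two binary covariates; chi-square against a logistic likelihood-ratio test.

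| Prevalences | Odds ratios | Unadjusted | Adjusted |
|---|---|---|---|
| 0.30, 0.10 | 1.5, 1.5 | 81.7% | 81.8% |
| 0.30, 0.10 | 2, 1.5 | 79.7% | 81.4% |
| 0.30, 0.25 | 2, 2 | 81.5% | 82.9% |
| 0.30, 0.10 | 3, 2 | 80.8% | 82.8% |
| 0.40, 0.30 | 3, 3 | 80.6% | 84.8% |
| 0.40, 0.20 | 4, 3 | 81.7% | 85.9% |
| 0.40, 0.30 | 4, 4 | 80.3% | 86.9% |

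The spread of the unadjusted column reflects simulation error (standard error √(0.8 × 0.2/3000) = 0.7 points). In the four settings that were also run with no effect (1.5/1.5, 2/1.5, 3/2 and 4/3), type I error was 4.9–5.4% unadjusted and 4.8–5.4% adjusted.

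**4. Simulation for the count.** With assumed Poisson counts and two covariates with rate ratios between 1.3 and 2, adding the covariates to a robust Poisson regression raised power by about 0 to 2 points, with type I error near 5%. The gain is larger at the top of that range if both covariates are also common.

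**5. Chance imbalance.** For a binary covariate with 30% prevalence, the SD of the between-arm difference is √(0.30 × 0.70 × (1/100 + 1/200)) = √0.00315 = 0.056. The chance of a gap above 10 points is 2 × (1 − Φ(0.10/0.056)) = 7.5%. It is 0.6% at 10% prevalence, 4.1% at 20% and 9.6% at 40%. A 10-point gap would shift the risk difference by about 1.0 point at odds ratio 1.5, 1.7 at 2, and 2.6–2.7 at 3, against the planned 17 points. In a sample with such a gap against the device, power is about Φ((0.17 − 0.017 − 0.1169)/0.0600) = 73% at odds ratio 2, and Φ((0.17 − 0.026 − 0.1169)/0.0600) = 67% at odds ratio 3.

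**The case against.** The unadjusted randomised comparison is valid, the design reaches about 81% power without adjustment, and the study calls itself a pilot and exploratory. On this view adjustment is optional. That largely stands, and it sets the severity.

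A reader might go further in four ways that the documents do not support.
- *The plan ignores strong predictors and wastes power.* No section gives a prevalence or a strength of association for any of these variables. Gains of 4 points or more appear only when two strong predictors are assumed. Frequent flying may be rare in a trial starting in September 2020 and run remotely because of the pandemic, and baseline TSS is capped below 9 in subjects without URI symptoms, which limits how much it can predict.
- *Chance imbalance biases or invalidates the comparison.* Over repeated randomisation it does neither; simulated type I error stays near 5%. The loss is in precision and in accuracy for the sample actually drawn.
- *The primary analysis is a chi-square or an ANOVA.* Section 10.0 does not say so. It assigns no test to the URI count.
- *Randomisation is simple.* The documents give only the ratio.

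It can also be objected that adjustment is not wholly free. A logistic odds ratio adjusted for covariates is conditional and does not correspond to the 50% against 33% contrast that sized the trial, and missing covariate values need a rule. Both are fair and are met in the fix.

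In favour of acting, the margin is thin: 300 − 294 = 6 subjects, and Section 5.0 states no allowance for dropout. With an assumed 5% loss, unadjusted power falls to 79.2%; with 10%, to 77.0%. Covariates explaining 2% of the variance would be worth about 6 subjects, and 5% about 16.

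**Conclusion.** The point holds as a minor efficiency improvement. Every comparison that Section 10.0 names is unadjusted, none is tied to the primary count, and plausible covariates already collected have no analytic role. None of the plan's figures is wrong on this account.

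The expected benefit is about 0 to 2 points of power for modest predictors and about 4 or more only if two are strong, together with correction for observed imbalance in the listed covariates. The conclusion rests on a two-sided 0.05 test, an 80% target that the plan does not state, and assumed prevalences and strengths. That no adjusted analysis is prespecified rests on the text alone.

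**What to change.** In Section 10.0:
- State that the primary analysis is a regression of URI count on arm, either Poisson with robust standard errors or negative binomial; choose one in advance.
- Adjust for a short fixed list: daily contact with young children, frequent flying, baseline TSS, and a single indicator for allergic rhinitis and/or chronic rhinosinusitis.
- Use the same list for any URI (yes/no), and report a marginal (standardised) risk difference so that the result matches the 50% against 33% contrast in Section 5.0.
- Keep the unadjusted result as a secondary display.
- Add a simple rule for missing covariate values, fixed before unblinding.

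The cost is SAP wording; every listed variable is already collected. The small downside is the missing-data rule and the discipline of keeping the list short.
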